1.3.13 Duration of project

Please refer to the attached timeline.

1.5 Links with other projects

This study is not linked with any other ongoing projects.

1.6 Problems Anticipated

One of the greatest concerns regarding this study is provider support. Providers at the Tampa Health Center will be required to permit support persons in the room.

Other potential problems include the potential frustration on the part of patients who may desire to have support person in the room but are not permitted to do so.

1.7 Expected outcomes of the study and dissemination of findings

This study aims to evaluate pain and anxiety levels in patients undergoing in-clinic abortion as well as assess provider and support person satisfaction when support person is in procedure room compared to when support person not in the procedure room. If this study demonstrates that having a support person in the room decreases pain and/or anxiety, this may help to support the inclusion of a support person in the procedure room and improve patient experience. In addition, if providers have a good experience, it may help allay provider concerns about having a support person in the room.

The final results will be presented at a national conference and submitted for publication in a peer-reviewed journal.

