1.1.2 Hypotheses and Objectives

Hypotheses:

Social support in the abortion procedure room will decrease perceived pain and anxiety levels and increase satisfaction for the patient.

- 1. Social support in the procedure room influenced the patient's health outcomes in the following areas:
 - 1. Decreased pain
 - 2. Decreased anxiety
 - 3. Increased patient satisfaction
- 2. The social support person will report that they were able to give effective support to the patient.
- 3. The physician and the nurse will find the support person effective in supporting the patient.

Null Hypothesis:

- 1. Social support in the abortion procedure room will not change patient levels of perceived pain, anxiety, or satisfaction.
- 2. The social support person will report they did not give adequate support.
- 3. The health care provider and the surgical assistant will not find the support person effective

in supporting the patient.

Objectives

Primary Aims:

- To assess a change in expected pain level from baseline, immediately after the procedure, and again ten minutes after arrival to the recovery room as determined by a 100mm visual analog scale (VAS) for patients with in-room social support during the procedure as compared to those who do not.
- To assess pre- and post-procedure state anxiety levels as determined by the 20-question State-Trait Anxiety Inventory (STAI) for patients with in-room social support as compared to patients without in-room social support.

Secondary Aims:

- To measure acceptability and effectiveness of having social support in the procedure room as reported by the surgical assistant and healthcare providers as determined by a post-procedure questionnaire.
- To evaluate if support was effectively given to the patient as reported by the support person as determined by a post-procedure questionnaire.

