1.3.2 Sample Size

A total of 400 subjects will be enrolled in this study; 200 participants will enroll in the control arm and 200 will enroll in the intervention arm. Within these two arms, 100 subjects will be "patients" and "support persons." "Patients" are defined as people who will receive an in-clinic abortion on the day of their participation. "Support persons" are the individuals whom the patient chooses to accompany them during the in-clinic abortion procedure. Support persons will only actually accompany patients in the in-clinic procedure room if they are randomized to the

intervention arm of this study. Health care providers will also be invited to participate in this research study—and enrollment numbers will depend upon the amount of unduplicated staff who will perform or assist with the D&C procedure on days when enrollment will occur. "Health care providers" include the physician performing the abortion and nurses assisting the physician within the abortion procedure room.

Prior studies indicate a 20mm difference in VAS is clinically significant and that the common standard deviation for VAS scores is 23 mm [8]. Based on these assumptions, a sample size of 28 with 14 women in each arm will have 90% power to detect at least a 20mm difference between the change in pain score from baseline, to during the procedure, to after the procedure between the two groups, using a Student's t-test evaluated at the 2-sided 0.05 significance level.

We have chosen a larger sample size to also provide a representative sample of our patient population for our secondary aims of patient and support person satisfaction as well as nurse and physician satisfaction. This sample size was calculated based on the total number of in-clinic abortion patients seen in the Tampa Health Center in 2015 with a Confidence Level of 95% and a Confidence interval of 10.

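### Two unranked primary aims and conflicting and/or wording let either pain or anxiety carry the conclusion, roughly doubling the false-positive risk if each is tested at 0.05

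*Protocol*

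**What the plan says.** Section 1.1.2 of the protocol has two entries under primary aims. The first concerns VAS pain, measured "from baseline, immediately after the procedure, and again ten minutes after arrival to the recovery room". The second is "To assess pre- and post-procedure state anxiety levels" with the STAI. Neither is ranked above the other, and neither post-procedure VAS time is marked as primary. The first null hypothesis in the same section bundles pain, anxiety and satisfaction into one statement of no change.

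Section 1.3.2 sizes the pain comparison with a t-test "evaluated at the 2-sided 0.05 significance level". That is the only significance level in the protocol, and it is attached to VAS alone.

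Section 1.3.11 compares the VAS change from baseline to the recovery room within each arm, then compares the change between arms without restating the time. It does not mention STAI by name and does not split or order alpha.

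Section 1.7 says that a finding that "having a support person in the room decreases pain and/or anxiety" may help to support having a support person in the room. The Project Summary makes a possible change in standard procedures depend on higher satisfaction together with lower pain and lower anxiety.

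**The concern.** The protocol words its conclusion in two ways that have different error properties. If all the named outcomes must improve, as the Project Summary reads, no adjustment is needed: the chance of a false overall claim cannot exceed that of any single test whose null is true. If one outcome is enough, as 1.7 reads, each additional test gives another chance of a false claim, and the overall error exceeds the level used for each test.

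The bundled null hypothesis in 1.1.2 fits the second reading, because a change in any one component contradicts it. With the aims unranked and no primary VAS time, the outcome that carries the conclusion could be picked after the results are seen. At stake is a claim that the protocol intends to publish and that it links to a possible change in clinic procedures.

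**Working it through.** **Inputs from the protocol.** Two-sided 0.05 for the VAS test, a 20 mm difference and SD 23 mm (1.3.2); VAS at two post-procedure times, and STAI (1.1.2). Enrolment of 200 subjects per arm is read as 100 patients and 100 support persons per arm (1.3.2).

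**Assumptions.** STAI is tested at the same two-sided 0.05. The protocol gives no correlation between outcomes, so a range is used.

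**The plan's own sample size.** n per arm = 2 × 23² × (1.960 + 1.282)² / 20² = 27.8, so 28 per arm. Section 1.3.2 states 28 in total, 14 per arm, for 90% power. With 14 per arm the normal approximation gives Φ(20 / (23 × √(2/14)) − 1.960) = Φ(0.341) = 63%. The stated figure is therefore not reproduced. This does not affect the present point, since planned enrolment exceeds both numbers.

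**Chance of at least one significant result in either direction, no true effect.** For k independent tests it is 1 − 0.95^k.

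- Two tests (one VAS contrast and STAI): 1 − 0.95² = 9.75%.
- Three tests (both VAS times and STAI): 1 − 0.95³ = 14.26%.

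**Chance of at least one false claim of benefit.** A two-sided 0.05 test has probability 0.025 in the favourable direction.

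- One test: 2.5%.
- Two tests: 1 − 0.975² = 4.9%.
- Three tests: 1 − 0.975³ = 7.3%.

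**Correlated outcomes.** Simulation of normal test statistics (4 million draws), with assumed correlations of 0.5 to 0.8 between the two VAS tests and 0.3 to 0.5 between VAS and STAI:

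| | Either direction | Benefit only |
|---|---|---|
| Two tests | 9.1% to 9.5% | 4.5% to 4.8% |
| Three tests | 11.5% to 13.3% | 5.8% to 6.7% |

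**Cost of the remedy for pain.** Power = Φ(20 / (23 × √(2/n)) − z), where n is the effective number per arm, z = 1.960 at 0.05 and z = 2.241 at 0.025 (the stricter Holm step for two tests). Allocation is by procedure day, so n is 100 divided by the day design effect. The documents give no figure for that, and the values 2 and 3 are assumptions.

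| Design effect | n | First term | Power at 0.05 | Power at 0.025 |
|---|---|---|---|---|
| 1 (no clustering) | 100 | 6.149 | above 99.9% | above 99.9% |
| 2 | 50 | 4.348 | about 99% | about 98% |
| 3 | 33.3 | 3.550 | about 94% | about 90% |

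The same calculation cannot be made for STAI, because the protocol gives no STAI difference or SD.

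**The case against.** The strongest reply is that the protocol contains no formal either-one rule. Section 1.7 is a dissemination paragraph with cautious wording and no test or level in it. The Project Summary and the lead hypothesis in 1.1.2 are worded jointly, and allocation of alpha is commonly left to a statistical analysis plan, which is not shown here. Pain and anxiety could also be reported as two separate claims.

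Much of this stands and limits the point. A reader might infer that the protocol fixes an either-one-wins rule at full alpha with an error of 10% to 14%. The documents do not support that, for four reasons.

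- 1.7 is not a decision rule.
- The 0.05 level is stated for VAS only.
- Three tests is one reading of 1.1.2. Section 1.3.11 names only baseline to recovery, and only for the within-arm test, so a single between-arm VAS contrast is equally possible.
- 14% requires three independent tests, which is implausible for two pain scores from the same patient.

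A reader might also infer that false claims of benefit occur at two to three times 5%. They do not: 1.7 speaks only of a decrease, so the relevant figures are about 5% for two tests or 6% to 7% for three, against 2.5% for one.

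The reply does not remove the point. The ranking of the primary aims, the primary pain time and the wording of the conclusion are matters this protocol itself addresses, and it leaves them unranked and inconsistent. An analysis plan that controlled alpha would still leave the Project Summary and 1.7 in conflict.

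**Conclusion.** The point holds in a limited form and should be corrected. If each primary test is run at two-sided 0.05 and either may carry the conclusion, the two-sided family-wise error is up to about 10% for two tests, or about 9% if they are correlated. If both VAS times are tested, it is at most about 14%, or about 11.5% to 13% under the assumed correlations. For false claims of benefit alone, the risk rises about twofold with two tests and somewhat more with three.

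These figures rest on three assumptions: 0.05 is applied to STAI, there is no multiplicity control elsewhere, and 1.7 rather than the Project Summary describes how the conclusion will be drawn.

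**What to change.** - In 1.1.2 and 1.3.11, name one between-arm VAS contrast, with its time, as the primary pain comparison and make the other time secondary.
- State how pain and STAI are tested together: either in fixed order, each at two-sided 0.05 with the second tested only if the first is significant, or with Holm over the two tests.
- Reword the Project Summary and 1.7 so that both describe the same conclusion and follow that rule.

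This takes a few sentences. The price is slightly less power for the adjusted or second test. For pain, power at 0.025 stays above 99.9% ignoring clustering by day and is about 98% if a day design effect of 2 is assumed. Under fixed order the first test loses nothing, but no confirmatory claim can be made on the second if the first fails.

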2. ETHICAL CONSIDERATIONS

This protocol will be submitted to the Chesapeake Institutional Review Board. The trial will also be approved by Planned Parenthood of Southwest and Central Florida (PPSWCF) and Planned Parenthood Federation of America's Clinical Research Department.

No effective health care will be withheld from study subjects. In clinical practice, support persons are not often allowed in the procedure room. If a patient states that she would prefer a support person in the room, but does not want to participate then she will not be eligible for the study and will then be able to have a support person in the procedure room only at the discretion of the provider.

2.1 Informed decision-making and confidentiality

Potential subjects interested in the study will be educated about the risks, benefits, and alternatives of study participation. All subjects will be encouraged to ask questions and all questions will be answered. The potential subject will be reminded that their participation is voluntary, and not participating in the trial will not alter the medical care that the patient will receive.

4. RESEARCH INSTRUMENTS/QUESTIONNAIRES

4.1 SUBJECT DEMOGRAPHIC QUESTIONNAIRE – INTERVENTION ARM

Please fill in the information below, if applicable: Age: _____ Gestational age (How many weeks pregnant are you?) Number of children: _____ Number of previous abortions: Religion: Please circle your answers below: Ethnicity: Hispanic Non-Hispanic Race: American Indian or Alaska Native Asian Black or African American Native Hawaiian or other Pacific Islander White Two or more races **Marital Status**: Single Married Divorced Widowed Separated Are you using your insurance for the procedure? No Yes Are you receiving sedation for the procedure? Yes No What is your relation to the patient/support person?

${\bf 4.1~SUBJECT~DEMOGRAPHIC~QUESTIONNAIRE-CONTROL~ARM}$

Please fill in the information below, if applicable:

Age:						
Gestational	age (H	ow many we	eks pregnant are	e you?)		
Number of	childre	n:				
Number of j	previou	ıs abortions:				
Religion:						
	your a	nswers below				
	Non-	Hispanic				
Race:	Ame	rican Indian o	or Alaska Native			
	Asia	n				
	Black	k or African A	American			
	Nativ	ve Hawaiian o	or other Pacific Isl	lander		
	Whit	e				
	Two	or more race	S			
Marital Sta	tus:	Single	Married	Divorced	Widowed	Separated
Are you usi	ng youi	r insurance f	or the procedure	?	Yes	No
Are you rec	eiving s	sedation for	the procedure?	Yes	No	
What is you	ır relati	ion to the pa	tient/support per	rson?		

4.2 POST-PROCEDURE QUESTIONNAIRE FOR PATIENT - INTERVENTION ARM Please circle your answers below:

1.	I would rate my overall satisfaction with the procedure as: Very satisfied
	Somewhat satisfied
	Neutral
	Somewhat dissatisfied
	Very dissatisfied
2.	The amount of discomfort I experienced during the procedure was acceptable. Definitely yes
	Probably yes
	Neutral
	Probably not
	Definitely not
3.	I feel that the amount of support I received from my support person in the procedure room helped decrease my pain. Definitely yes
	Probably yes
	Neutral
	Probably not
	Definitely not
4.	I feel that I received all the support I needed from my support person in the procedure room. Definitely yes
	Probably yes
	Neutral
	Probably not
	Definitely not
La	st updated: 4/10/2017

5. The presence of my support person in the procedure room made me feel uncomfortable.
Definitely yes
Probably yes
Neutral
Probably not
Definitely not
6. If you were uncomfortable in the procedure room, were you uncomfortable due to any of the following: (Circle all applicable options)
- Facility (ex. too cold, too small, uncomfortable chair, etc)
- Staff (instructions, attentiveness, respect, etc.)
- Beliefs (religious ideology, aversion to medical procedures, etc.)
- Other:
- Not applicable
Please provide any additional information:
7. During my procedure with my support person in the room, I felt concerned about the following: (Please circle all that apply) Privacy
Security
Other:
Not applicable

8. If I had to re-live this experience, I would prefer/choose to be accompanied in the procedure
room again.
Definitely yes
Probably yes
Neutral
Probably not
Definitely not
9. Do you have any additional comments or concerns about having a support person in the procedure room?
Thank You!

$\textbf{4.3 POST-PROCEDURE QUESTIONNAIRE FOR PATIENT-CONTROL\ ARM}$

Please circle your answers below:

1.	I would rate my overall satisfaction with the procedure as: Very satisfied
	Somewhat satisfied
	Neutral
	Somewhat dissatisfied
	Very dissatisfied
2. T	the amount of discomfort I experienced during the procedure was acceptable. Definitely yes
	Probably yes
	Neutral
	Probably not
	Definitely not
3. I pair	believe that having a support person in the procedure room would have helped decrease my
1	Definitely yes
	Probably yes
	Neutral
	Probably not
	Definitely not
4. If	I had to re-live this experience, I would prefer/choose to be accompanied in the procedure m.
	Definitely yes
	Probably yes
	Neutral
	Probably not
	Definitely not

5. Do you have any additional comments or concerns about having a support person in the procedure room?				
		Thank You!		

4.4 VISUAL ANALOG SCALE (VAS)

For these questions we are going to ask you to make an X on a line. For example, let's say you are asked how much you like Oreo cookies:

How much do you like Oreo cookies? (Make an X on the line)

very very little much

Answer the question by making an "X" on the line according to how much you like or dislike Oreo cookies. If you liked Oreo cookies a lot, then you might make an "X" on the line like so:

very / very little / much

If you liked Oreo cookies more than life itself(!), then you might make an "X" on the line like so:

very Very little Very

If you hated Oreo cookies, then you might make an "X" like so:

very very little much

If you thought Oreo cookies were just "OK," then you might make an "X" like so:

very Very little much

The idea is that if you like Oreo cookies, you make an "X" on the line closer to the phrase "very much." The closer you make the "X," the more you are saying you like Oreo cookies. If you don't like Oreo cookies, you make an "X" on the line closer to the phrase "very little." The closer you make the "X," the more you are saying you don't like Oreo cookies.

Please mark an X on the line to indicate your response to the following questions.

1. How much pain do you think you will have during procedure?	
no	worst pain
pain	in my life
ACTUAL TIME OF ASSESSMENT::	
2. How much pain you are having now (immediately at the end oprocedure)?	of the abortion
no	worst pain
pain	in my life
ACTUAL TIME OF ASSESSMENT::	
3. How much pain you are having now (in the post-abortion recent	overy room)? worst pain
	worst pain
pain	in my life
ACTUAL TIME OF ASSESSMENT:	

4.5 POST-PROCEDURE QUESTIONNAIRE FOR SUPPORT PERSON- INTERVENTIONPlease circle your answers below:

1) I had a clear understanding of my role as a support person during the procedure.
Definitely yes
Probably yes
Neutral
Probably not
Definitely not
2) I feel I provided effective support to the patient in the procedure room.
Definitely yes
Probably yes
Neutral
Probably not
Definitely not
3) I feel that the patient was comforted by my presence in the room. Definitely yes
Probably yes
Neutral
Probably not
Definitely not
4) I was comfortable in the procedure room.
Definitely yes
Probably yes
Neutral
Probably not
Definitely not
Don't know/no opinion
Last updated: 4/10/2017

5) If you felt uncomfortable in the procedure room, were you uncomfortable due to any of the following: (circle all that apply)
- Facility (ex. too cold, too small, uncomfortable chair, etc)
- Staff (ex. instructions, attentiveness, respect, etc.)
- Beliefs (ex. religious ideology, aversion to medical procedures, etc.)
- Other:
- Not applicable
Please provide additional information:
6) Based on my experience today, I would serve as a support person during an abortion procedure again.
Definitely yes
Probably yes
Neutral
Probably not
Definitely not
Don't know/no opinion
10) Do you have any additional comments or concerns about being a support person in the procedure room?

Thank You!

${\bf 4.6~POST\text{-}PROCEDURE~QUESTIONNAIRE~FOR~SUPPORT~PERSON\text{-}~CONTROL}$

Please circle your answers below:

1. I had a clear understanding of what my role as a support person would have been during the procedure.
Definitely yes
Probably yes
Neutral
Probably not
Definitely not
2. I feel I would have provided effective support to the patient in the procedure room.
Definitely yes
Probably yes
Neutral
Probably not
Definitely not
3. I feel that the patient would have been comforted by my presence in the room. Definitely yes
Probably yes
Neutral
Probably not
Definitely not

4. I believe I would be comfortable being in the procedure room during the in-clinic abortion procedure.
Definitely yes
Probably yes
Neutral
Probably not
Definitely not
Don't know/no opinion
5. Do you have any additional comments or concerns about being a support person in the procedure room?
Thank You!

$\begin{tabular}{ll} \textbf{4.7 POST-PROCEDURE QUESTIONNAIRE FOR HEALTH CARE STAFF-INTERVENTION ARM \\ \end{tabular}$

Please circle your answers below:

1.	The presence of the support person in the procedure room was helpful to me.
	Definitely yes
	Probably yes
	Neutral
	Probably not
	Definitely not
2.	The presence of a support person in the procedure room was helpful to the patient.
	Definitely yes
	Probably yes
	Neutral
	Probably not
	Definitely not
3.	I felt uncomfortable with the support person's presence in the procedure room.
	Definitely yes
	Probably yes
	Neutral
	Probably not
	Definitely not
4.	During the patient's procedure, I felt concerned about the following due to the support person's
	presence: (Please circle all that apply)
	Privacy; please specify
	Security; please specify
	Other
	Not applicable
Las	st updated: 4/10/2017

	Ple	ase prov	e additional information:							
				-						
5)	I felt tha	ıt I had t	provide support to the support person in the procedure room.							
	Definit	ely yes								
	Probab	ly yes								
	Neutra	1								
	Probab	ly not								
	Definit	ely not								
6)	companiment in the procedure room to become a permanent arrangen	nent.								
	Definite	ly yes								
	Probabl	y yes								
	Neutral									
Probably not										
Definitely not										
	Don't kı	Don't know/no opinion								
7)	MVA:									
	YES	or	NO							
8)	Complica	ations:								
	YES	or	NO							
	Do you h	-	lditional comments or concerns about having a support person in the							
			Thoule Voy							
Las	st update	ed: 4/10	Thank You! 017							

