1.3.8.3 Health Care Staff Questionnaires

- 1) Before the health care staff participates in the study- they will undergo informed consent and sign a copy of the informed consent form. Health care staff who choose not to participate will be informed that they will not receive any negative consequences for not participating. A copy of the informed consent form will be provided to the health care staff.
- 2) After each procedure, the physician, and nurse, and other health center staff in the abortion procedure room caring for the patient will complete a post-procedure questionnaire.
- 3) The complete questionnaires will be manually entered in the Qualtrics data management software which will only be managed by designated research staff. Study documents, including surveys, will be stored in a locked filing cabinet and will be accessed by research personnel only.

A sample of the demographic survey, STAI, VAS, and the post-procedure questionnaires for the patient, support people, and health care staff is attached at the end of this proposal (see section 4).

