1.3.11 Data Analysis

Analysis will be performed using Qualtrics statistical software. Analyses will be performed on all control and experimental group data. The control group is defined as the standard care without presence of support person, whereas the intervention group is all those receiving standard care with the presence of a support person in the procedure room. Demographic, behavioral, and clinical characteristics will be compared between the two arms using frequency tests, Student's ttest, chi-squared tests, and two-way ANOVA, where appropriate. The change in pain score, as assessed by VAS, from baseline to recovery room will be compared within each group using paired Student's t-test if the data are normally distributed or Wilcoxon signed-rank test if the data do not follow a Gaussian distribution. Similarly, the difference in the change in VAS scores between the

study arms will be compared using Student's t- or Mann-Whitney U tests, where appropriate. Questionnaire answers will be compared between both arms of the study using chi-squared statistical analysis. Statistical analysis will be performed by both the Principal Investigator and statistician.

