4.8 POST-PROCEDURE QUESTIONNAIRE FOR HEALTH CARE STAFF - CONTROL ARM

Please circle your answers below:

Last updated: 4/10/2017

1.	The presence of the support person in the procedure room would have been helpful to me. Definitely yes
	Probably yes
	Neutral
	Probably not
	Definitely not
2.	The presence of a support person in the procedure room would have been helpful to the patient Definitely yes
	Probably yes
	Neutral
	Probably not
	Definitely not
3.	I would have felt uncomfortable with the support person's presence in the procedure room. Definitely yes
	Probably yes
	Neutral
	Probably not
	Definitely not
4	4. During the patient's procedure, I believe I would have concerns in the following areas if the
5	support person was present: (Please circle all that apply)
	Privacy; please specify
	Security; please specify
	Other
	Not applicable
	Please provide additional information:

28

	accompanied by a support person, I feel like I would have had to provide or the support person.
Definitely yes	
Probably yes	
Neutral	
Probably not	
Definitely not	
6. I would like the ac	ecompaniment in the procedure room to become a permanent arrangement
Definitely yes	
Probably yes	
Neutral	
Probably not	
Definitely not	
. MVA:	
YES or	NO
3. Complications:	
YES or	NO
9. Do you have any a procedure room?	additional comments or concerns about having a support person in the

Thank You!

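### Staff item 6 offers a don't-know answer on the intervention form only, so its planned between-arm chi-squared comparison can differ because of the form

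*Protocol*

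**What the plan says.** Staff acceptability is a secondary aim in Protocol 1.1.2: "To measure acceptability and effectiveness of having social support in the procedure room as reported by the surgical assistant and healthcare providers". Under 1.3.8.3 the physician, the nurse and other staff in the room "caring for the patient will complete a post-procedure questionnaire" after each procedure. There are two versions of the form, 4.7 for intervention days and 4.8 for control days.

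Item 6 is on both. On 4.8 its statement is about accompaniment "in the procedure room to become a permanent arrangement", followed by five graded answers, and the next item (MVA) comes straight after. On 4.7 the statement survives only in part ("companiment in the procedure room to become a permanent arrangen"). Its five graded answers are followed by a sixth: "Don't know/no opinion".

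Section 1.3.11 fixes the analysis: "Questionnaire answers will be compared between both arms of the study using chi-squared statistical analysis". It gives no rule for an answer that only one arm can record.

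**The concern.** Staff items 1 to 5 describe what happened on the intervention form and what would have happened on the control form. Item 1 on 4.8, for example, asks whether the support person's presence "would have been helpful to me". Item 6 is not recast in this way, so a reader would naturally compare the arms on it.

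The answer lists differ, however. An undecided staff member can say so on an intervention day but must choose one of the graded answers, perhaps Neutral, on a control day. A contingency table of item 6 by arm then has a column that must be empty in the control arm. Chi-squared counts that structural zero as evidence of a difference. What is at stake is a misleading result on one item of a secondary aim.

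**Working it through.** The protocol states no figure on this point, so there is none to reproduce. The check compares the forms and then works through an illustration.

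**Comparing the forms**
- 4.7, item 6: five graded answers plus the don't-know answer, six in all.
- 4.8, item 6: five graded answers, then the MVA item.
- Support persons' comfort item (item 4 on both 4.5 and 4.6): the don't-know answer is on both forms. Leaving it off is therefore not a general convention of the control forms.

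**Inputs**
- Section 1.3.2 states that "200 participants will enroll in the control arm and 200 will enroll in the intervention arm", read as 100 patients and 100 support persons per arm, hence 100 procedures per arm.
- One staff form per procedure gives 100 forms per arm; physician and nurse both answering gives 2 × 100 = 200.
- Assumed, not in the protocol: identical opinion in both arms, independent forms, and a share d of intervention forms marked don't-know.

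**Illustration: d = 10%, remaining answers spread evenly, 200 forms per arm**
- Control: 40 in each of five answers, 0 don't-know. Intervention: 36 in each of five, 20 don't-know.
- Expected count per arm: (40 + 36)/2 = 38 for each graded answer; (0 + 20)/2 = 10 for don't-know.
- X² = Σ(O − E)²/E = 10 × 2²/38 + 2 × 10²/10 = 1.05 + 20 = 21.05 on 5 df, p = 0.0008.
- With 100 forms per arm every count halves and so does X²: 10.53 on 5 df, p = 0.062.

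Nearly all of this comes from the don't-know column. With equal numbers of forms per arm and k don't-know answers, all in one arm, that column contributes 2 × (k/2)²/(k/2) = k.

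**Allowing for sampling variation.** The two values above are computed at expected counts. The test was also simulated (20,000 runs, 5% level) with an assumed opinion split of 30/25/25/12/8%. Don't-know answers were drawn either proportionally from all answers or only from Neutral. Share of runs that reject although opinion is identical:

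| Use of don't-know | 100 forms per arm | 200 forms per arm |
|---|---|---|
| 2% | 0.08 | 0.18–0.19 |
| 5% | 0.27–0.31 | 0.77–0.81 |
| 10% | 0.79–0.87 | about 1.00 |

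With the same options on both forms, the simulated rate at 100 forms per arm is 0.050.

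**Dropping don't-know answers at analysis.** If they were drawn evenly from all answers, the remaining shares are undistorted. If they came from Neutral, the rejection rate at 100 forms per arm (noncentral chi-squared) is 0.07 at 5% use, 0.17 at 10% and 0.43 at 15%. At 10% use the combined yes share rises from 55% to 0.55/0.90 = 61% with no real difference.

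**The case against.** The text is damaged at this point. The opening words of item 6 on 4.7 are lost, so that the two statements match is an inference. This stands as a caveat. The sixth answer on 4.7 is legible, and the list on 4.8 looks complete, so a lost sixth option is unlikely; the PDF can settle it.

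The magnitude is assumed. Neither 10% use nor the even spread is in the protocol, and at 100 forms per arm the illustration itself gives p of about 0.06. This stands too. A reader might infer that the test on item 6 will pick up the form and not opinion. The protocol supports only that it can, if staff use the option.

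Forms are not independent. Section 1.3.12 mentions a small number of rotating providers, and the same people may answer repeatedly, in both arms. The p-values and rejection rates above are therefore illustrative. That is a separate problem, which matching the options does not solve.

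Handling of don't-know answers could be set in an analysis plan that is not shown, and an empty column would be visible in any table. This is fair, but a rule at analysis is only a partial cure if those respondents would otherwise have chosen Neutral.

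Two further readings go too far. One is that item 6 bears most directly on changing clinic practice. The Project Summary ties such change to patient satisfaction, pain and anxiety, and section 1.7 ties support for the practice to pain and/or anxiety, with provider experience only possibly easing provider concerns. The other is that between-arm tests of items 1 to 5 should be barred. Their hypothetical wording is a different question and does not follow from a missing answer option.

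**Conclusion.** The mismatch is real on the forms as read, and section 1.3.11 applies a test that is sensitive to it. The conclusion is conditional: if staff use the don't-know answer, the item 6 comparison can show a difference made by the form. Under the stated assumptions the effect runs from negligible near zero use, through a rejection rate of 0.08 at 2% use with 100 forms per arm, to near-certain rejection at 10% use with 200. The protocol does not say where in that range the trial would fall. This is a minor point, worth correcting because the correction is nearly free.

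**What to change.** Check item 6 on forms 4.7 and 4.8 in the original PDF. If the mismatch is confirmed, give the item the same answer options on both forms before the first enrolment, either by adding the don't-know answer to 4.8 or by removing it from 4.7. Either choice removes the structural zero.

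If forms are already in use, state how don't-know answers will be handled before the data are examined, and report their number. Merging them with Neutral restores comparability only if those respondents would otherwise have chosen Neutral.

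The cost is a one-line form edit, with no change to sample size, visits or respondent burden.
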